Observations of screening and recruitment will be conducted by UH Research Credentialed study staff. The study coordinator or research assistant who recruit patients in the ED will introduce the additional study staff and explain that they are observing the interactions and taking notes. They will be given the opportunity to verbally refuse to be observed during consent. The consent form will also have an option to opt out of further observation of study procedures. Study staff in the ED, including the acupuncturists, will provide written consent ahead of time to be observed during the observation site visit.

Provider Feasibility Survey Consent Process:

We will use staff rosters to identify physicians, nurse practitioners, physician assistants, nurses and ED staff who have been employed by in the ED at one of the three sites during the data collection period. A recruitment email will be set via REDCap to invite participation. Providers and staff who are interested will click a link to the feasibility study information sheet. Those who wish to participate will click “yes” and be directed to the survey. Up to 4 reminder emails will be sent.

We will also distribute a recruitment flyer in the ED at each site, inviting ED providers and staff to participate. The flyer will include a QR code that links directly to the study information sheet. Those who wish to participate will click “yes” and be directed to the survey. A \$5 incentive will be provided to participants who complete the feasibility survey. Contact information to send the incentive will be collected in a separate REDCap form from the survey to maintain confidentiality.

Randomization

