4. What is your race? Check all that apply.
 - a. American Indian or Alaska Native
 - b. Asian
 - c. Black or African American
 - d. Native Hawaiian or other Pacific Islander
 - e. White
 - f. Other [FREE TEXT]
 - g. Decline to answer
5. What is your Age?
 - a. ____ years
6. How long have you worked in an ED?
 - a. ____ months
7. What is your occupation?
 - a. Nurse,
 - b. APP,
 - c. resident,
 - d. attending physician,
 - e. other if other [FREE TEXT]
8. Did you have any direct contact with the ACUITY study?
 - a. No
 - b. Yes
- 8a. if yes please briefly describe the specific contact you had with the ACUITY study or ACUITY staff [FREE TEXT]
9. Have you ever received acupuncture?
 - a. No
 - b. Yes

9a. IF yes, please do your best to recall about how many times you have received acupuncture

- a) 1 time
- b) 2-4 times
- c) 5-10 times
- d) 11-15 times
- e) 16 or more times

We have two questions about your opinion of acupuncture in general—as a treatment in the ED.

1. Do you view acupuncture in general as an appropriate intervention for the ED setting? (Likert scale (1-very appropriate—5-Very inappropriate)
2. Do you view acupuncture in general as helpful in managing patient pain in the ED? (Likert scale (1-Very helpful—5- Not at all helpful)

We also have two questions about your opinion of how the ACUITY research project was delivered in your ED.

[figure not shown]
1. Were you satisfied with how the ACUITY acupuncture intervention was delivered in your setting? (Likert scale (1-Very satisfied—5-Very dissatisfied)
2. Did the ACUITY project impose a burden on ED staff in your setting?
 - 1 – Not a burden
 - 2 – Somewhat of a burden
 - 3 – Moderate burden
 - 4 – Extreme burden

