6.2 Description of Evaluations

6.2.1 Screening Evaluation

At each ED, the Study Coordinator (SC) or Research Assistant (SC) and acupuncturist will work as a team, staffing an average 2.5, 4-6 hour recruitment/intervention sessions per week, varying the times

and days across sites as this may influence adoption. As in Figure 1, after the ED RN conducts the initial triage activity, the SC or RA (“study staff”) will identify and conduct initial eligibility pre-screening in the in the ED triage unit. The patient will then be roomed and seen by the ED clinical provider. If the ED provider determines that patient does not have a clinical condition prohibiting study participation, s/he will sign a study approval form (see below). The study staff will then approach the patient for study participation.

Provider sign off

Acupuncture in the Emergency Department for Pain Management (ACUITY)

If the patient is randomized to the acupuncture arm, please withhold pain and anxiety medications until after the acupuncture session.

The study coordinator will inform you what arm they are assigned to and when their session has ended.

In order for this patient to be eligible to participate in the "Acupuncture in the ED" study, please verify you have examined the patient and believe to the best of your knowledge, at this time, that the patient does not have the following conditions:

Critical status / Trauma
 Bone fracture
 Joint dislocation
 Migraine
 Psychological / psychiatric concern
 Clinical judgement / Other:

If you deem the patient eligible for the study, the patient will be randomized to acupuncture or usual care.

Patient can continue in study
 Patient is excluded from study

Sign: _____

Consenting Procedure

We have requested a partial HIPAA waiver for prescreening. Therefore, patients will only be consented once the screening process is over and eligibility is confirmed.

The consent process will occur after the patient has gone through the triage process and been assigned to a room within the ED. The consent process will be conducted by dedicated research staff (SC or RA) that have been trained in obtaining informed consent and who have current Human Subjects Protection and Good Clinical Practice certifications. The status and location of the patient will be monitored by

research staff using the EHR to ensure the patient is approached at an appropriate time.

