6.3 Provider Feasibility Assessment

A recruitment email will be sent via REDCap to invite participation. Providers and staff who are interested will click a link to the feasibility study information sheet. Those who wish to participate will click "yes" and be directed to the survey. We will also distribute a recruitment flyer in the ED at each site, inviting ED providers and staff to participate. The flyer will include a QR code that links directly to the study information sheet. Those who wish to participate will click "yes" and be directed to the survey. Feasibility surveys will be completed online by interested participants at their convenience.

- Demographic information including: gender, ethnicity, race, age, how long they have worked in the ED, occupation, contact with the ACUITY study and in what context
- If the provider has ever received acupuncture and if so, how often
- General opinion about acupuncture
 - Do you view acupuncture in general as an appropriate intervention for the ED setting? Likert scale (1-very appropriate—5-Very inappropriate)
 - Do you view acupuncture in general as helpful in managing patient pain in the ED? Likert scale (1-Very helpful—5- Not at all helpful)
- Delivery of ACUITY study in the ED
 - Were you satisfied with how the ACUITY acupuncture intervention was delivered in your setting? Likert scale (1-Very satisfied—5-Very dissatisfied)
 - Did the ACUITY project impose a burden on ED staff in your setting? Not a burden, Somewhat of a burden, Moderate burden, Extreme burden

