At ED discharge, 1-week and 4-week follow-up, all participants will be asked to answer; “How satisfied are you with how your pain was managed during your ED visit” on the 5-point Likert scale. A second question is “Overall how satisfied are you with your treatment during your ED visit?” on the same Likert Scale. At the end of enrollment, the SC or RA at each site will contact ED staff to complete a brief survey (via REDCap) to assess their general satisfaction with the acupuncture intervention by answering “Do you view acupuncture in general as an appropriate intervention for the ED setting?” Likert scale (1-very appropriate—5-Very inappropriate) and “Do you view acupuncture in general as helpful in managing patient pain in the ED?” Likert scale (1-Very helpful—5- Not at all helpful). *And two questions regarding the delivery of ACUITY study in the ED:* “Were you satisfied with how the ACUITY acupuncture intervention was delivered in your setting?” Likert scale (1-Very satisfied—5-Very dissatisfied) and “Did the ACUITY project impose a burden on ED staff in your setting?” Not a burden, Somewhat of a burden, Moderate burden, Extreme burden. We will compare across sites and across patient groups (e.g. pain location, patient demographics etc). We will calculate the proportion of subjects answering each question and 95% exact CI across sites as well as across patient groups such as different presenting complaints and patient demographics. We will assess variables across different provider characteristics (including age, race, sex), and across the study sites.

Fidelity

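### The two survey items on how ACUITY was delivered go to ED staff with and without study contact, and the analysis plan does not separate the two groups

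*Combined protocol and SAP*

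**What the plan says.** **Who is surveyed.** Section 4.3 (Provider Feasibility Survey Consent Process) sets the frame: "We will use staff rosters to identify physicians, nurse practitioners, physician assistants, nurses and ED staff who have been employed by in the ED". This covers each participating ED while data are being collected. The section adds a second, open route: "We will also distribute a recruitment flyer in the ED at each site, inviting ED providers and staff to participate". Neither route requires contact with the study.

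**What is asked.** In the survey printed in Section 6.1, item 8 reads "Did you have any direct contact with the ACUITY study" and takes No or Yes, with a free-text follow-up (8a) for 'Yes'. Two items on acupuncture in general come later, then two on the study itself: "Were you satisfied with how the ACUITY acupuncture intervention was delivered in your setting" (five points) and "Did the ACUITY project impose a burden on ED staff in your setting" (four categories). Section 6.3 lists "contact with the ACUITY study and in what context" with the demographic information.

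**What is analysed.** Section 9.6 (Aim 2b1) defines acceptability among ED staff, for the quantitative assessment, as how satisfied they are with the acupuncture as it was delivered in their department. Section 9.5 (Acceptability) states: "We will calculate the proportion of subjects answering each question and 95% exact CI across sites". It also promises breakdowns by provider characteristics, naming age, race and sex as examples, and by site. Contact is not named there or in Section 9.6.

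**The concern.** A respondent with no contact may have no basis for rating how the intervention was delivered. Every response option shown is a substantive rating, so such a respondent must either rate something not seen or leave the item blank. The reported proportion is then a mixture of informed and uninformed answers, and its value depends on how many of each happened to reply.

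Three uses of the data are exposed:

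- **The headline figures** for staff satisfaction and burden.
- **The comparison across sites.** Sites whose exposed staff hold the same views could appear to differ only because their contact shares differ.
- **The mixed-methods analysis** in Section 9.6, which uses survey answers to form groups of providers who do and do not find the protocol acceptable. Uninformed answers could put people in the wrong group.

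**Working it through.** The documents give no sample size, expected response, contact share or target for this survey, so there is no stated figure to reproduce.

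**1. Is a filter shown?** The survey marks its conditional items: 8a and 9a both depend on a 'yes'. The follow-up form in Appendix B also marks its branches. The two delivery items carry no such mark. 'Decline to answer' is offered for sex, gender, ethnicity and race, but no opt-out is shown for the delivery items. A figure is missing from the available text just before these items, so branching cannot be ruled out entirely.

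**2. Is 'no contact' a realistic answer?** Section 6.2.1 describes teams "staffing an average 2.5, 4-6 hour recruitment/intervention sessions per week".

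- Weekly presence: 2.5 × 4 = 10 h to 2.5 × 6 = 15 h. Of 168 h, that is 6.0% to 8.9%.
- Enrolment per site: 50 + 5 pilot = 55 patients over 6 to 9 months (Sections 3 and 9.2). 55/26 weeks = 2.1 per week; 55/39 weeks = 1.4 per week.
- Sessions per site over the whole period: 2.5 × 26 = 65 to 2.5 × 39 = 97.5, about 98.

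The first two lines make no-contact respondents plausible. The third shows why weekly hours do not measure staff exposure: over 65 to 98 sessions, with staff rotating, cumulative contact could be common. The contact share cannot be derived.

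**3. What could pooling do?** With contact share c:

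pooled proportion = c × p(contact) + (1 − c) × p(no contact)

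Assume that 50% of contacted staff report some burden. All shares and rates below are assumptions, for illustration only.

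| Burden reported by no-contact staff | c = 25% | c = 50% | c = 75% |
|---|---|---|---|
| 0% | 12.5% | 25% | 37.5% |
| 50% | 50% | 50% | 50% |
| 70% | 65% | 60% | 55% |

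For example, 0.25 × 0.50 + 0.75 × 0.70 = 0.65. With c = 1, which is what restricting to item 8 = 'Yes' gives, every row returns 50%.

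**4. Site comparison.** From the first row, two sites with the same 50% among contacted staff but contact shares of 25% and 75% would show 12.5% and 37.5%, a gap of 25 percentage points that reflects contact alone.

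**5. Direction for satisfaction.** If no-contact staff all answer neutral, the formula with p(no contact) = 0 applies to the proportion satisfied and equally to the proportion dissatisfied. Both fall. Whether that flatters the study depends on what contacted staff think.

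**The case against.** A reader might infer that the plan pools all answers and so will dilute both results towards a favourable picture, with the 6.0% to 8.9% of weekly hours as a guide to how strongly. The documents do not support that reading.

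- **The plan does not commit to a pooled figure only.** Its list of provider characteristics is open-ended, and contact is collected with the demographics, so a split by item 8 needs no new data. This stands. The gap is that the split is permitted but not specified, which leaves the choice of headline open until the results are known.
- **Direction and size are not established.** This stands, as steps 2, 3 and 5 of the working show. The survey is also voluntary, so respondents need not mirror the roster.
- **The burden item asks about ED staff in the setting**, not about the respondent. Someone with no direct contact may have watched colleagues' workload change, and 'direct contact' is not defined. This stands, and it argues against hiding the item from 'No' respondents.
- **The live survey is not shown.** The revision summary for version 6 calls the printed form a sample, and a figure is missing at this point. This stands as a matter for the sponsor to confirm.
- **The stakes are limited.** The outcome is secondary, no decision threshold rests on it, and acceptability is also explored in interviews whose sample includes providers of enrolled patients. This stands and sets the weight of the point. It does not make the survey percentages interpretable without the split.

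**Conclusion.** On the text shown, the two delivery items are put to all respondents whatever their contact, and no contact-based denominator or stratum is specified. The satisfaction and burden proportions, the site comparisons and the mixed-methods groups may therefore be distorted by people who did not see the delivery. The size and direction are unknown. The 12.5% to 65% range against 50% rests wholly on assumed rates and a 25% contact share, and there is no distortion if both groups answer alike.

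The conclusion assumes that the live survey has no branch on item 8 that the available text fails to show. The damage is recoverable, because item 8 is collected. This is a cheap improvement, not a threat to the trial's primary outcomes.

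**What to change.** 1. Confirm whether the REDCap survey branches on item 8.
2. **Satisfaction with delivery:** specify item 8 = 'Yes' as the main denominator and show 'No' respondents separately.
3. **Burden:** keep asking everyone, and report the 'Yes' and 'No' strata side by side, because the item concerns staff in the setting.
4. Carry the same split into the site comparisons, and state which respondents may define the mixed-methods groups.
5. If the survey is not yet fielded, add a 'no basis to judge' option to both items.
6. Leave the two general-opinion items for all respondents.

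The cost is a short addition to the analysis plan, one extra response option on two items, and smaller numbers with wider exact intervals for those items. If the survey has already been fielded, steps 2 to 4 can still be done with the data collected.

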6.2 Description of Evaluations

6.2.1 Screening Evaluation

At each ED, the Study Coordinator (SC) or Research Assistant (SC) and acupuncturist will work as a team, staffing an average 2.5, 4-6 hour recruitment/intervention sessions per week, varying the times

and days across sites as this may influence adoption. As in Figure 1, after the ED RN conducts the initial triage activity, the SC or RA (“study staff”) will identify and conduct initial eligibility pre-screening in the in the ED triage unit. The patient will then be roomed and seen by the ED clinical provider. If the ED provider determines that patient does not have a clinical condition prohibiting study participation, s/he will sign a study approval form (see below). The study staff will then approach the patient for study participation.

Provider sign off

Acupuncture in the Emergency Department for Pain Management (ACUITY)

If the patient is randomized to the acupuncture arm, please withhold pain and anxiety medications until after the acupuncture session.

The study coordinator will inform you what arm they are assigned to and when their session has ended.

In order for this patient to be eligible to participate in the "Acupuncture in the ED" study, please verify you have examined the patient and believe to the best of your knowledge, at this time, that the patient does not have the following conditions:

Critical status / Trauma
 Bone fracture
 Joint dislocation
 Migraine
 Psychological / psychiatric concern
 Clinical judgement / Other:

If you deem the patient eligible for the study, the patient will be randomized to acupuncture or usual care.

Patient can continue in study
 Patient is excluded from study

Sign: _____

Consenting Procedure

We have requested a partial HIPAA waiver for prescreening. Therefore, patients will only be consented once the screening process is over and eligibility is confirmed.

The consent process will occur after the patient has gone through the triage process and been assigned to a room within the ED. The consent process will be conducted by dedicated research staff (SC or RA) that have been trained in obtaining informed consent and who have current Human Subjects Protection and Good Clinical Practice certifications. The status and location of the patient will be monitored by

research staff using the EHR to ensure the patient is approached at an appropriate time.

All potential participants will be examined by an ED provider to ensure they do not need emergent care and have sufficient mental capacity to participate in the study. If the ED provider determines that patient does not have a clinical condition prohibiting study participation, s/he will sign a study approval form. Research staff will assess patient capacity to understand and sign study documentation prior to obtaining consent. If patient is capable to continue research staff (SC or RA) will consent potential participants. In doing so, they will explain the study, including benefits, risks and interventions. The research staff will stress to the patient that participation is voluntary and they may withdraw from the study at any time. Consent decline or withdrawal from the study will not affect the patient's continued care in the ED. As per other studies conducted by the PI, the research staff will be trained to answer all questions that may arise. Privacy will be ensured by conducting all study related interactions, including the consent process, within the patient's private ED treatment room. Patients will be provided ample time to go through the consent process and ask any questions. Time for decision making will be minimized due to the fast-paced and urgent nature of the ED. After a member of the research staff explains the consent form, study requirements and answers all of the patient's questions about the study, patients will provide written consent. Only the participating patients themselves will be allowed to provide consent for inclusion into the study. No legally authorized representative (LAR) may enroll a patient into the study. Study activity may only continue after the patient has provided written consent. If a patient declines to participate or is unable to sign consent documents, a reason for refusal will be asked and documented in the study database. It will be considered a declination of participation if a patient refuses to provide study staff with their phone number and email address during the baseline assessment. Patients who decline participation will not be allowed to opt into the study for the remainder of that particular ED visit. However, they would be eligible to participate at a future ED visit if interested and if the study is still in the recruitment phase. If a patient enrolls in the study, he or she will no longer be eligible for study participation during future ED visits within the recruitment period. We will utilize the EHR, and the 21 CFR Part 11 compliant data collection tool (e.g., REDCap), to verify the patient has not previously participated in the study.

Documentation of Informed Consent will follow Connor Integrative Health Network's Standard Operation Procedures (SOP) for Obtaining Informed Consent and Re-Consent, which includes a Research Informed Consent Documentation template. The Documentation form captures the date and time of consent, the name of the study and IRB number, name of person consenting, individuals present during consent process, the names of anyone else involved in the decision making process, the name of the staff member obtaining informed consent, if the subject verbalized understanding of the study, if the consent process happened in a private setting, if the subject received a copy of the signed consent, etc. This form will be signed by the person obtaining consent and by the PI and retained with the original copy of the signed consent.

Screening

All screening activities must be completed before consent and study enrollment. Consent and study enrollment will happen shortly after screening given the nature of the ED environment and emergent nature of the patients' acute pain. Study staff will use the EHR and information from the triage nurse to determine initial eligibility. All potential participants will be examined by an ED provider to ensure they do not need emergent care and have sufficient mental capacity to participate in the study. If the ED provider determines that patient does not have a clinical condition prohibiting study participation, s/he will sign a study approval form.

6.2.2 Enrollment, Baseline, and/or Randomization

Enrollment

Subjects are considered enrolled once the informed consent document has been signed and randomization has occurred. Only one written informed consent document will be used, as we have

requested a partial HIPAA waiver for screening.

Baseline Assessments

- Pre-Treatment Pain Intensity Assessment (Pre) using a 0-10 NRS^{58,59} will be collected: a) for acupuncture patients, before administration of acupuncture; b) for usual care patients who receive a pain medication order within 60 minutes (+/- 15 minutes) of being roomed, just before or at administration of pain medication; or c) for usual care patients who have not received a medication order within 60 minutes (+/- 15 minutes) of being roomed, at 60 minutes (+/- 15 minutes). The collection time window of 60 minutes was based on median time from being roomed to first pain medication (54 minutes) using data obtained from the ANW ED pilot study (See Figure 1). Pre-treatment pain assessments will be timed to be completed immediately prior to the administration of either the acupuncture or usual care treatments.
- Anxiety scores using a 0-10 NRS^{58,59}
- Expectancy will be measured with the following questions.
 - By the end of the treatment period in the ER, how much improvement in your pain symptoms do you think will occur?
0% 10% 20% 30% 40% 50% 60% 70% 80% 90% 100%

Now, please close your eyes for a few moments and try to identify what you really feel about the treatment and its likely success. Then answer the following questions:

- At this point, how much do you really feel that the treatment will help you to reduce your pain symptoms?
1 2 3 4 5 6 7 8 9
Not at all Somewhat Very much
- By the end of your treatment period in the ER, how much improvement in your pain symptoms do you really feel will occur?
0% 10% 20% 30% 40% 50% 60% 70% 80% 90% 100%

Randomization

Immediately after screening, obtaining informed consent from eligible patients, and collecting baseline data, the study staff will randomize patients to either Acupuncture or Usual Care.

